5.3 Provider Randomization Assignment Procedures

5.3.1 Randomization Procedures

Randomization will occur before the trial begins. All eligible providers will be block randomized to ensure comparable numbers of patients enrolled in each study arm. Providers will be categorized according to the expected number of patients for whom they will issue a qualifying prescription during the study period. The expected number of qualifying prescriptions will be determined given past prescribing behavior and department or specialty. Information on past prescribing behavior may vary across study sites based on available provider data but will generally include the absolute number of qualifying prescriptions as well as the rate of qualifying prescriptions (per number of visits billed or number of unique patients seen, as available). Providers in certain departments may also be more likely to write qualifying prescriptions. For example, providers who specialize in mental or behavioral health or providers in clinics focusing on higher risk adolescents. The particular departments associated with more qualifying prescriptions will be identified separately for each health system based on previous prescribing patterns and knowledge of that health system.

Providers in each health system will be divided into as few as two randomization blocks (likely and unlikely prescribers) and as many as four randomization blocks (unlikely, likely, high frequency, and very high frequency) based on the total number and distribution of expected number of qualifying prescriptions. For example, KP Washington providers wrote fewer than 100 qualifying prescriptions in the yearlong interval examined and the distribution of qualifying prescriptions per provider had a long right tail indicating that a small number of physicians wrote a large number of qualifying prescriptions. In this

context, we defined four groups for block randomization to protect against a large imbalance in the number of patients enrolled across study arms.

R, an open-source statistical computing software, will be used to generate an even number of control and intervention assignments within each provider block.

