divided by the rate on control, estimated by Poisson regression) and 95% two-sided confidence interval (CI) will be compared to the non-inferiority margin (overall: $M = 1.5$) and non-inferiority of the algorithm approach will be declared if the entire coverage of the 95% CI is less than 1.5.

In safety review reports, the ratio between arms of emergency department visit rates will be accompanied by a confidence interval and by the non-inferiority margin, 1.5, for reference. Confidence intervals will be defined by estimating the rate ratio in 5,000 bootstrap samples. Resampling will be done on the cluster (provider) level and stratified by the presence of any event within each cluster. Quantile-based confidence intervals will be identified using the appropriate percentile corresponding to the Pocock alpha-spending function for interim analyses. Excess harm is observed if the entire coverage of the confidence interval for the rate ratio comparing the greater to the lesser rate of emergency department and urgent care visits is greater than 1.5. (While the final non-inferiority analysis for this safety outcome will use the robust sandwich estimator to ensure correct standard errors, the properties of this estimator are based on asymptotic behavior and small sample size performance may be poor.)

We anticipate initial follow-up of 800 patients, randomized to the two arms, with 720 patients remaining enrolled in the study at 6 months of follow-up (i.e., 10% lost to follow-up). Assuming a $P < 0.05$ alpha level, and based on an anticipated 95% of patients in the control arm using antipsychotics at 6 months, this sample will ensure over 95% power to detect a 6% reduction in the percent of participants with any order for antipsychotic medications at 6 months. Furthermore, we expect to have 80% power to detect a 13% reduction in subgroups with exposures occurring with 25% prevalence, and 80% power to detect a 17% reduction in subgroups with exposures occurring with 18% prevalence (e.g., racial/ethnic minorities). A minimal clinically important difference of 10% was pre-specified to allow for evaluation of clinical significance as well as statistical significance. We have over 90% power to detect a 10% reduction in antipsychotic use at 6 months for patients in the intervention arm given a rate of 85%, 90%, or 95% use in the control arm.

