Inferential analysis for this outcome will estimate **the odds ratio (OR) of AP use observed at 6 months** between intervention and control. For this analysis, we will use a logistic regression model where the outcome is a binary indicator of AP use observed at 6 months. Binary treatment arm assignment and any inpatient hospitalization in the prior year will be the only covariates

Analysis plan for Safety Use of Antipsychotics in Youth (SUAY)

included in the regression model. The estimated coefficient associated with treatment is interpreted as the log-OR of observing AP use at six months for an intervention patient vs. a control patient. Patient is the unit of analysis, GEE will be used to account for correlation within provider, and robust standard errors (with working independence covariance matrix assumed) will be calculated to construct a 95% CI around the estimated OR. Our null hypothesis is that the OR is equal to 1, corresponding to no statistically significant difference between AP use observed at 6 months. We will reject the null hypothesis if the lower bound of the 95% CI is above 1 (increased use in treatment arm) or the upper bound is below 1 (decreased use in treatment arm).

Variables	Definition	Present/Absent
taking_at_6mon	Using AP at 6 months (No (0)/Yes(1))	present
groupn	Randomization Group - use for descriptive stats (Intervention (1)/Control(2))	present
group_cat	Randomization Group - use in models (Control (0)/Intervention (1))	present
prior_hosp	Prior Hospitalization (No (0)/Yes(1))	present

Sensitivity analysis will be conducted using similar approach as mentioned above, we will perform the following separate analyses related to our primary outcome by:

- % of patients taking antipsychotic medications (measured by orders) at 6 months post enrollment, using the minimum based on SIG reviews
- % of patients taking antipsychotic medications (measured by orders) at 6 months post enrollment, using the maximum based on SIG reviews
- % of patients taking antipsychotic medications (measured by prescription fills) at 6 months post enrollment. Note that this analysis may be performed using three healthcare systems (KPWA, KPCO, and KPNW) due to limitation in data availability

Variables	Definition	Present/Absent
taking_at_6mon_min	Using AP at 6 months - minimum (No (0)/Yes(1))	present
taking_at_6mon_max	Using AP at 6 months - maximum (No (0)/Yes(1))	present
taking_at_6mon_fills	Using AP (fills) at 6 months (No (0)/Yes(1))	present

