Descriptive analysis will summarize **the rate of AP use**, calculated as the days' supply (maximum of 181) ordered divided by follow-up time (time until end of enrollment or 181 days), Calculation of cumulative prescription fill ordered should be censored at 181 days. For example, if the only AP order for a patient is a 30 days' supply at, for e.g., 160 days post-enrollment, the total days' AP supply during follow-up should be recorded as 20 days (181 days -160 days) because we only want to capture AP use during the 6 months post-enrollment. In the case that total days' AP supply exceeds health plan enrollment that is, if a patient disenrolls from the health system with outstanding medication in hand, the total days' AP supply will include AP orders after disenrollment. For example, if a patient had an AP order after disenrollment on day 170 (a 30 days' supply), the total days' AP supply during follow-up should be recorded as sum of AP orders before day 170 and AP orders after day 170. Similarly, the offset should be increased to equal the last day with medication on hand (with a maximum for 181 for both).

Inferential analysis will estimate the **relative risk (RR) of AP use between intervention and control** during the 6 months post-enrollment. For this analysis, we will use Poisson regression where the outcome is the total days' AP supply (maximum of 181) for each enrolled patient and the offset is the number of days follow-up. For the primary analysis, treatment arm and inpatient hospitalization in the prior year will be the only covariates included in the regression model (additional covariate adjustment will be done as a sensitivity analysis), and the estimated coefficient for treatment arm is interpreted as the log-RR of AP use for an intervention patient vs. a control patient. Patient will be the unit of analysis for this regression model, and the regression model will be fit using generalized estimating equations (GEE) to account for correlation within provider. We will estimate standard errors using a robust (sandwich) covariance estimation (assuming a working independence covariance structure) and construct a 95% confidence interval (CI) around the estimated RR. Our null hypothesis is that the RR is equal to 1, corresponding to no statistically significant difference between AP order rates in

Analysis plan for Safety Use of Antipsychotics in Youth (SUAY)

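### The provider-clustered sandwich intervals have no finite-sample correction, and the plan does not give the provider numbers needed to judge whether one is needed

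*SAP*

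**What the plan says.** Providers are the randomised unit. Protocol 5.3.1 allocates them within each health system, in two to four blocks of expected prescribing volume, and patients take the arm of their prescriber (Protocol 5.2).

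The SAP's Primary analysis I is a logistic GEE clustered on provider, in which "robust standard errors (with working independence covariance matrix assumed) will be calculated to construct a 95% CI around the estimated OR". Primary analysis II is a Poisson GEE with an offset, of which the SAP says "We will estimate standard errors using a robust (sandwich) covariance estimation (assuming a working independence covariance structure". In both, the null is rejected when the 95% interval excludes 1. Arm and prior-year hospitalisation are the only covariates; site enters only in sensitivity analyses. Secondary analyses I, II, III and VII also use GEE with robust standard errors. None of these names a finite-sample correction, a t reference or a minimum number of providers.

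Two Protocol passages bear on this. Section 5.3.1 reports that at KP Washington, with fewer than 100 qualifying prescriptions in a year, "a small number of physicians wrote a large number of qualifying prescriptions", and uses this to justify four blocks there. Section 8.2.1 plans a provider-level bootstrap for interim emergency-department safety reports. It explains that, although the sandwich is kept for the final analysis of that outcome, "the properties of this estimator are based on asymptotic behavior and small sample size performance may be poor".

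**The concern.** The sandwich estimates variance from the squared residual totals of the clusters. It is reliable when there are many clusters and none dominates. A provider with a large share of an arm pulls the fitted arm mean towards its own result, so its residual, and with it the standard error, comes out too small. Blocking on volume balances the arms but does not raise the effective number of clusters.

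Since rejection rests on the interval alone, under-coverage would turn directly into a type I error above 5% for the primary comparisons. The documents do not give the three inputs needed to judge this: the number of enrolling providers, their patient counts and the within-provider correlation.

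**Working it through.** **The plan's own figures.** No coverage or clustering figure is stated; the nearest is the power table in Protocol 8.2.1. With pooled variance, two-sided 0.05 and independent patients, power = Φ{[|d| − 1.96√(2p̄q̄/n)] / √[(p₁q₁ + p₂q₂)/n]}. For 75% v 85% with n = 360: (0.10 − 1.96 × 0.02981)/0.02958 = 1.405, so power is 92.0%, as stated. The eight rows give 84.5, 99.5, 96.5, 92.0, 78.5, 81.7, 66.8 and 62.3%, against 80, >99, 97, 92, 80, 80, 67 and 62% stated. Seven agree within 2 points; the first agrees only with a continuity correction (80.9%). The table therefore reproduces with no design effect and implies nothing about provider numbers.

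**Inputs from the documents.** 800 patients enrolled, "with 720 patients remaining enrolled in the study at 6 months of follow-up (i.e., 10% lost to follow-up"; provider as cluster; independence working covariance; nominal 95% interval.

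**Inputs assumed.** Number of enrolling providers K, size distribution, correlation and outcome level.

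**Formulas** (arm-only models; prior hospitalisation omitted). With e_i the residual total of provider i in arm g:
- Logistic: V = Σ_g Σ_i e_i² / [N_g p_g(1 − p_g)]².
- Poisson: V = Σ_g Σ_i e_i² / T_g², where T_g is the arm's total days.
- Planned interval: estimate ± 1.96√V.
- Mancl-DeRouen: replace e_i by e_i/(1 − h_i), where h_i is the provider's share of its arm, and use t on K − 2.
- Effective number of providers: (Σn_i)²/Σn_i².

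Example: a provider with 115 patients in an arm of 360 has h = 0.319, so its squared residual is multiplied by 1/(0.681)² = 2.16.

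**Simulation A, logistic.** 800 patients; outcome 0.6 or 0.9; correlation 0.05–0.15; lognormal size weights (sigma 1.0, 1.5); even allocation in four size strata; 2,500 runs per setting (Monte Carlo error about ±0.9 points). A repeat run is in brackets. The last two columns add four sites with allocation within site and assumed site outcomes. Type I error of the uncorrected interval, %:

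| K | Effective number | No site differences | Sites 52.5–67.5% | Sites 45–75% |
|---|---|---|---|---|
| 250 | 70–128 | 5.5–7.9 (5.3–7.6) | 4.6–6.9 | 4.0–5.6 |
| 150 | 37–71 | 5.8–9.0 (6.2–8.7) | 5.0–8.9 | 3.9–7.5 |
| 100 | 25–46 | 6.6–11.2 (6.2–11.3) | 5.3–8.3 | 3.9–7.6 |

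With Mancl-DeRouen and t on K − 2, error was 4.7–6.4% (4.2–6.7%) without site differences and 2.6–5.5% with them. A further set at correlation 0.10, with allocation within site and volume block and 100–250 providers, gave 5.6–10.4% without and 4.2–11.1% with site differences, against 3.0–6.0% corrected.

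**Simulation B, logistic and Poisson.** About 720 patients; correlation 0.02–0.10; 3,000 (logistic, outcome 0.90) or 1,500 (Poisson) runs per setting. Coverage of the uncorrected 95% interval, %:

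| K | Equal sizes | Weights 1/rank^0.7 | Weights 1/rank |
|---|---|---|---|
| 20 | 90–93 | 86–90 | 81–85 |
| 40 | 93–95.5 | 89–92 | 84–88 |
| 80 | 93–95.5 | 90.5–93 | 87–91 |
| 160 | 93–95.5 | 93–94.5 | 89–92 |
| 300 | 93–95.5 | 93–94.5 | 89–93 |

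Under 1/rank weights the effective number is only 8 at K = 20 and 29 at K = 300. Corrected coverage was 92.9–96.9% (logistic) and 92.8–96.7% (Poisson) over all settings.

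**The case against.** The strongest reply is that the harm is conditional.

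- **Concentration.** A reader might infer that trial enrolment is concentrated in few providers. The documents describe past prescribing at one site, and Protocol 5.3.1 allows other sites as few as two blocks. No trial-wide distribution is given.
- **The Protocol's caveat.** A reader might infer that the Protocol doubts the sandwich for its final analyses. It does not: the caveat explains the bootstrap in interim safety reports, and the same sentence keeps the sandwich at the end. Different methods at interim and final are not a contradiction.
- **Site.** Allocation is within site but the primary models omit site, so the sandwich counts between-site variance that the design has removed. That pushes intervals the other way. This stands, but it is not a dependable safeguard: with site differences, error still reached 7.6% in one set of runs and 11.1% in another.
- **Emergency-department test.** A reader might extend the result to the non-inferiority test. That outcome was not simulated, so no claim is made.
- **The remedy.** A t reference on K − 2 uses the nominal provider count; at 100 providers it is 1.98 against 1.96, so the residual adjustment does most of the work. The correction can be conservative (down to 2.6%). Carrying over a provider bootstrap is tempting, but a percentile version gave 5.4–6.8% at 250 providers and 5.5–9.5% at 100, little better than the sandwich, so it is not proposed.
- **Timing.** The SAP already notes that age differs significantly between arms, so some arm comparisons had been made when it was last edited. A late change should not displace the planned interval.

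**Conclusion.** This is a cheap improvement, not a demonstrated error. The plan's wording implies the standard sandwich, with no safeguard against few or unequal clusters. If enrolment is long-tailed, the 95% intervals are likely too narrow: type I error is about 5.5–8% with 250 enrolling providers and about 5–11% with 100. With 40 or more similar-sized providers, or 160 or more with a moderate tail, coverage is about 93–95.5% and little is lost. Large site differences can bring the error to about 5%, or below it.

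It would be too strong to say that the intervals are too narrow: that rests on provider counts, patient distribution, correlation and site differences that the documents do not give. The simulated outcome levels were 0.6 and 0.9, not the 95% control rate used for power. The case for acting is that, without site differences, the uncorrected interval erred mainly towards false rejection, while the corrected one stayed near nominal, or somewhat conservative with site differences.

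**What to change.** State in the SAP that GEE standard errors use a bias-corrected sandwich (for example Mancl-DeRouen) with a t reference on the number of enrolling providers minus 2. Report the number of enrolling providers per arm and the variation in patients per provider, so that readers can judge how far the correction matters. If outcome results by arm have already been seen, keep the planned interval and report the corrected one beside it, labelled as added later.

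The cost is a sentence in the SAP, a software option and a descriptive table. Intervals will be slightly wider, and mildly conservative if site differences are large.

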Follow up patient outreach: If the teen/family agree to BH navigation, the navigator will initiate contact at least monthly during the 6 month follow up period to inquire about the child's status and re-evaluate barriers to access. The navigator will use motivational interviewing techniques (e.g., reflective listening, asking open ended questions) with the youth and/or parents to encourage them to engage in psychosocial treatments, attempt to motivate them to continue or restart therapy (as needed), and identify and help problem-solve ways to minimize barriers to starting or continuing therapy. When barriers exist, s/he will offer assistance in identifying behavioral health clinicians that may be a good fit for the family/teen, and further assess appropriateness of short-term bridging therapy.

The navigator will remind teens/families, as appropriate, that laboratory tests are due to be completed 3 months after starting an antipsychotic.

The navigator will note any medication side effect information incidentally reported by the teen/family in the phone note. If a reported side effect is burdensome, the navigator will encourage the patient or parent/guardian to contact their provider about their concern or side effect.

The navigator will follow the study *Safe Practice Protocol* if suicidal ideation is incidentally revealed by a subject during a BH navigation outreach call.

Ad hoc patient outreach: The navigator will reach out to assess barriers and attempt to motivate the teen/family to continue therapy if a BH appointment is missed and not rescheduled within 2 weeks.

Final patient outreach call: The navigator will conclude services with a review of the agreed upon plan for next steps and encouraging continued contact with the clinical care delivery system.

Follow up provider outreach: Following each outreach call, the navigator will secure message the prescriber with relevant updates, as needed.

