7.5 Short-Term Bridging Therapy Description

Either the study CAP or the prescribing clinician may decline bridging therapy for the subject based on the clinical scenario. The BH navigator will use a decision tree to further assess appropriateness of short-term bridging therapy. Any reason that bridging is not offered will be noted in the navigator's reporting workbench (e.g., declined by prescriber, CAP advised against, subject already engaged in therapy, etc.).

The BH navigator will administer modified oral consent/assent for bridging services, as required by the local IRB, schedule the initial session, and note if the teen/family requires a loaner device (e.g., tablet) if bridging visits are to be delivered via telemental health (TMH) video visits.

When TMH is to be delivered, a TMH privacy and safety plan with the subject prior to the first TMH session. The offer of TMH will be suspended if a privacy or safety concern is identified when the form is completed until a clinical decision can be made by the therapist. The plan identifies resources within and outside the home to ensure patient privacy during TMH sessions, and plan for any potential crises, safety concerns, or inability to contact the teen/family.

All bridging visits will be entered in Epic as patient visits. There will be no copays or other charges billed for these study-related visits.

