Patient enrollment in the study occurs when a provider writes a qualifying antipsychotic prescription for an eligible adolescent patient or enters a patient reported medication (these two actions are indistinguishable in Epic). (Eligibility is confirmed by study staff following enrollment.) Follow-up time after enrollment extends for 6 months (181 days). Some patients will not remain enrolled in the health plan for a full six months, censoring follow-up, and the number of days covered in the health plan post-study enrollment should be recorded. If patients have a health care plan enrollment gap that is less than 45 days, they will be considered as having continuous enrollment in the study (i.e. not loss to follow up). For example, if a patient has a gap in their healthcare plan enrollment for less than 45 days during the study, this patient will be considered to have continuous enrollment. However, if there is an enrollment gap in their healthcare plan for at least 45 days, the patient will be disenrolled from the study at the healthcare plan disenrollment day. Note that, since patients do not have to be enrolled with a specific health care plan to be seen at NCH, we will assume a full follow up time of 6 months (181 days). Follow-up time should be indicated in the analytic dataset for all enrolled patients.

Analysis

Primary analysis I

Our primary analysis examines the percentage of patients taking antipsychotic medications (measured by provider medication orders) at 6 months post enrollment

Descriptive analysis will summarize **the percent of patients observed to be using AP at 6 months**, defined by presence of days' supply AP ≥ 181 days or medication in hand at 6 months. For example, if a patient has a 30-day supply order on or after 151 days post-enrollment, that patient has AP medication "in hand" at 6 months. Note: a patient does not have to have ≥ 181 days' total supply during the study to have medication in hand at 6 months. We will not adjust for loss to follow-up or disenrollment for this outcome definition. Patients who do not have prescription fill information up to 6 months post-baseline due to health plan disenrollment will have AP use observed at 6 months if they have AP orders after disenrollment that is ≥ 181 days. For example, if a patient disenrolls at day 160 and has a AP order (30 days' supply) after disenrollment, they have medication "in hand" at 6 months

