group	Randomization Group – use for restricted descriptive stats (Intervention/Control)	present
group_cat	Randomization Group – use in models (Control (0)/Intervention (1))	present

Analysis plan for Safety Use of Antipsychotics in Youth (SUAY)

p_offset	Number of days of follow-up for primary analysis (using orders)	present
prior_hosp	Prior Hospitalization (No (0)/Yes(1))	present
provider_type	Provider type of the enrolling provider, based on specialty (Non-Mental Health (0)/Mental Health (1))	present

- We will adjust for some baseline covariates in the model – site only, site and age (since significantly different by intervention and controls), and site and baseline covariates.

Variables	Definition	Present/Absent
person_days	Person-days on AP (orders) during 180 Day Follow-up Period (using orders)	present
group_cat	Randomization Group (Control (0)/Intervention (1))	present
p_offset	Number of days of follow-up for primary analysis (using orders)	present
prior_hosp	Prior Hospitalization (No (0)/Yes(1))	present
site	Study site (KPCO (1)/KPWA (2)/KPNW(3)/NCH (4))	present
provider_type	Provider type of the enrolling provider, based on specialty (Non-Mental Health (0)/Mental Health (1))	present
age_emanicip	Emancipated age according to state (No (0)/Yes(1))	present
gendern	Gender (Male (1)/Female (2))	present
race_AA	Either race variable is African American/Black (No (0)/Yes(1))	present
race_AllOth	All other racial/ethnic groups (does not include white, black or unknown) (No (0)/Yes(1))	present
Hispanic	Hispanic ethnicity (No (0)/ Yes (1))	Present
insuranceType	Type of insurance (Commercial/Medicaid/Other)	present
new_enrollee_1	new health enrollee (1 st definition) Yes/No	present

- ~~Depending on the rate of cross-over, we will perform cross-over analysis that compares patients who switched from one provider in one arm to another provider in a different arm~~
- For the total number of days in the study, instead of using disenrollment date, we will use the date of the last encounter as the last day in study

Variables	Definition	Present/Absent
person_days	Person-days on AP (orders) during 180 Day Follow-up Period (using orders)	present
group_cat	Randomization Group (Control (0)/Intervention (1))	present
s_offset	Number of days of follow-up for sensitivity analysis (using last encounter date)	absent
prior_hosp	Prior Hospitalization (No (0)/Yes(1))	present

Analysis plan for Safety Use of Antipsychotics in Youth (SUAY)

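### The last-encounter sensitivity analysis of days on antipsychotic lets study contacts lengthen follow-up in the intervention arm only, and its numerator and offset can end on different dates

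*SAP*

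**What the plan says.** The SAP's Primary analysis II models total days' supply ordered, up to 181, by Poisson GEE with working independence. The offset is days of follow-up. Follow-up ends at disenrollment or day 181, and under Health plan enrollment and follow-up time every patient at NCH is given the full 181 days.

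One listed sensitivity analysis changes the end date: "instead of using disenrollment date, we will use the date of the last encounter as the last day in study". Its variable table pairs s_offset, marked absent, with the same person_days variable that the primary analysis uses. No version of person_days that stops at the last encounter is listed. The SAP does not say what counts as an encounter, and it gives no cap, no day-count convention and no rule for patients whose only encounter is the enrolling one.

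For the primary offset, the SAP covers patients who leave the plan with supply outstanding: "Similarly, the offset should be increased to equal the last day with medication on hand", up to 181. It calls the sensitivity analyses similar in approach, but does not say whether this rule carries over to s_offset.

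The protocol describes contacts that only one arm receives. Section 5.3.2 states that study psychiatrists, navigators and therapists deal with intervention patients only. Section 7.5 says: "All bridging visits will be entered in Epic as patient visits". Section 7.4 says that, for families who accept, "the navigator will initiate contact at least monthly during the 6 month follow up period". Navigator activity is recorded in phone notes (7.4) and in an Epic reporting workbench (7.4.1, 14.2). Neither document says whether these records are encounters.

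**The concern.** An offset should measure time at risk in the same way in both arms. Here it ends at an event that the intervention can itself generate after randomization. If study contacts count, intervention patients appear to be followed for longer, their person-time rises and their rate falls, with no change in prescribing.

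Separately, if person_days runs to day 181 while the offset stops earlier, the ratio is no longer a proportion of days covered. A patient with 90 days ordered and a last encounter on day 10 would have a rate of 9 days per day.

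What is at stake is a robustness check on a primary outcome. It alters follow-up most at NCH, where full follow-up is assumed. If it is biased toward benefit, it could be read as supporting or enlarging an effect.

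**Working it through.** No figure in either document rests on s_offset, so there is nothing to reproduce. The check asks what the analysis returns when antipsychotic use is identical in the two arms.

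**Formula.** With arm as the only covariate and working independence, each arm's rate is (sum of days' supply) / (sum of offsets). With equal supply in both arms:

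RR = mean offset in control / mean offset in intervention.

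For example, if the control mean is 140 days, an intervention mean longer by 5, 10 or 20 days gives 140/145 = 0.966, 140/150 = 0.933 or 140/160 = 0.875.

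**Late study contacts counted, supply rule not applied.** Assumptions, none of them in the documents: non-study encounters are Poisson with mean spacing d days, and a fraction p of intervention patients have a counted study contact uniform on days 150 to 181. Then:

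- Without a late contact, mean last-encounter day = 181 − d(1 − e^(−181/d)).
- With a late contact, mean = 181 − [d − (d²/31)(1 − e^(−31/d))].

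| Non-study visits | Mean without | Mean with | RR at p = 20% | 40% | 60% |
|---|---|---|---|---|---|
| 0.5 per month (d = 60) | 123.9 | 167.9 | 0.93 | 0.88 | 0.82 |
| 1 per month (d = 30) | 151.1 | 169.7 | 0.98 | 0.95 | 0.93 |
| 2 per month (d = 15) | 166.0 | 172.3 | 0.99 | 0.98 | 0.98 |

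Worked entry, d = 60 and p = 40%: intervention mean = 0.6 × 123.9 + 0.4 × 167.9 = 141.5, and 123.9/141.5 = 0.88.

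**Same, with the supply rule applied.** The offset becomes the later of the last encounter and the last day covered. Assume further that 10% have no order, 30% are covered to day 181 and 60% have coverage ending uniformly between days 30 and 181. At d = 60 the control mean is 152.4 days. At p = 60% the intervention mean is 164.3, so RR = 152.4/164.3 = 0.93. More frequent usual care, lower uptake or longer coverage moves this toward 0.99.

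**Null simulation with clustered standard errors.** Assumptions: 360 patients and 90 providers per arm, monthly navigator calls at 50% uptake, about half of patients persisting on drug to 6 months, prior hospitalization omitted, zero offsets dropped, 600 runs per scenario. False benefit means the upper 95% limit falls below 1 (nominal 2.5%, simulation error about 0.6 points). Columns are the mean number of usual encounters in 181 days.

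| Scenario | 2 | 4 | 8 |
|---|---|---|---|
| Calls count, supply rule not applied: RR (false benefit) | 0.926 (32%) | 0.958 (16%) | 0.984 (6.5%) |
| Calls count, supply rule applied: RR (false benefit) | 0.964 (22%) | 0.981 (10%) | 0.996 (3.5%) |

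- At 25% uptake without the supply rule, RR is 0.962, 0.980 and 0.994.
- If only bridging visits count, RR is 0.996 to 1.012 and false benefit 1.7% to 3.8%. Bridging sessions close together end well before day 181. If they are spread out, a separate check gave RR of about 0.95 to 0.995.
- Without the supply rule, 46% to 63% of patients have a numerator larger than their offset.

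**Remedies tested in the same simulation.**

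- Excluding study contacts: RR 0.998 to 1.004, false benefit 1.7% to 3.7%.
- Keeping study contacts but cutting the numerator at the same date: RR 0.989 to 0.994, false benefit 3.8% to 5.5%.
- Setting zero offsets to 1 day, with study contacts still counted and the numerator uncut: RR 0.862 and false benefit 76% at a mean of 2 encounters.

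**The case against.** The strongest reply has four parts.

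1. The only study contact documented as a patient visit is bridging, which stops after at most 9 sessions, and by itself it produces little or no bias when sessions come early. Material bias needs navigator calls, or other late contacts, to be logged as encounters, and the documents do not say that they are. This stands, and it is why the size is conditional. It does not remove the problem, because navigator activity is recorded in Epic and no exclusion is written.

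2. The SAP's supply rule may carry over. If it does, rates above 1 cannot occur. A reader might infer from the variable table that the offset is plainly undefined for patients who never return. The documents do not support that as a general statement. It needs day-0 counting and no supply rule. With inclusive counting the offset is 1 day. With the rule, only patients with neither an order nor a later encounter are affected (about 1% in the simulation at a mean of 2 encounters). Against carry-over, the SAP ties the rule to disenrollment, the very date replaced here, and describes s_offset as "Number of days of follow-up for sensitivity analysis (using last encounter date"). Even if it carries over, the difference between arms shrinks but remains.

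3. A reader might call this the only check on full follow-up at NCH. That is too strong. The fill-based analysis may be run in the three other systems with its own offset, which removes the NCH assumption, although it also changes the data source.

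4. This is one of several sensitivity analyses, and the decision rule uses p_offset. That is correct and limits the consequence. Direction is also not certain in general: if control patients use more drug, refill visits could lengthen control follow-up.

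**Conclusion.** The point holds in conditional form. As listed, the analysis allows an offset that the intervention can lengthen and pairs it with a numerator that need not end on the same date. With no true effect, the rate ratio would be roughly 0.82 to 0.98 if late navigator contacts count, roughly 0.93 to 0.99 if the supply rule also applies, and close to 1.00 if only early bridging visits count. With frequent usual care (about 8 encounters in 181 days) the bias is small in every case. Visit frequency, uptake, persistence on drug and the recording of navigator calls are all assumptions.

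A reader should not infer that the primary result is biased, or that this analysis must show a false benefit. The documents support neither. What they show is a robustness check whose result could not be interpreted as it is now specified.

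**What to change.** Amend the SAP text for this sensitivity analysis as follows:

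- Define the last encounter from non-study encounters only, by the same rule in both arms. Drop bridging visits and navigator contacts, and cap the date at day 181.
- Make numerator and offset end on the same date. Either cut person_days at the last encounter, or state that the supply rule for the primary offset also applies to s_offset.
- Do not rely on a 1-day minimum offset. State the day-count convention, and report by arm the number of patients with no encounter after enrollment. The SAP's own example counts day 160 to day 181 as 20 days, whereas 181 − 160 = 21, so the convention needs settling in any case.

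The cost is a few lines of SAP wording and a derived variable, using contacts that the study already tracks. Follow-up in this one analysis becomes shorter. System visits prompted by the navigator may still differ by arm and should be stated as a limitation. The absent flag on s_offset does not prove that the analysis is still to be run, and the SAP already mentions an observed age difference between arms. If the analysis has been run, repeat it this way, label the change as post hoc, and do not cite the earlier result as support.
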